6.4.2. Radiological Response

Radiological responses will be assessed by DRC and by investigator and will be be classified as (complete response, partial response, stable response, and failure.

Number and percentage of patients in the mITT Populations with radiological responses at EOST as determined by the DRC will be tabulated for Cohort A. -Two-sided 80% exact binomial CIs of the treatment success (complete and partial response) rate will be presented for Cohort A.

Radiological responses at EOST as determined by the Investigator will be tabulated in the same manner.

6.4.3. Mycological Response

Mycological responses will be assessed by DRC and by investigator and will be classified as eradication, presumed eradication, persistence, or indeterminate.

Number and percentage of patients in the mITT Populations with mycological responses at EOST as determined by the DRC will be tabulated for Cohort A. Two-sided 80% exact binomial CIs of the treatment success (eradication and presumed eradication) rate will be presented for Cohort A.

Mycological responses at EOST as determined by the Investigator will be tabulated in the same manner.

6.4.4. Clinical Signs and Symptoms

Clinical signs and symptoms will be summarized at Baseline and study visit. Number and percent of participant with each clinical signs and symptoms of absent, mild, moderate, severe, or not done will be presented.

6.4.5. Next Generation Sequencing of Cell-free Pathogen DNA

DNA sequencing was to be performed by a reference genetic laboratory (Karius) to facilitate the identification of infecting pathogens; subject level listing will be provided.

A subject level listing of for (local lab investigator site) and (central LAB) will be provided.

6.4.7. Fungal Culture

A subject level listing by pathogen will be provided for local (investigator site) and central laboratory results.

6.4.8. Radiology Assessments

A subject level listing of imaging results will be provided.

6.6. Pharmacokinetic Assessment

All pharmacokinetic analyses will be performed by an external laboratory vendor and described in a standalone PK analysis plan.

6.7. Subset Analyses

The following sub-group analysis will be provided for primary and key secondary endpoint:

- Primary endpoint: Day 42 mortality by baseline pathogen.
- Secondary endpoint: global response at EOST by baseline pathogen.
- Primary endpoint: Day 42 mortality by limited treatment option criteria.
- Secondary endpoint: global response at EOST by limited treatment criteria.
- Primary endpoint: Day 42 mortality by participant who switch to 400 mg BID fosmanogepix dose vs. maintained with 800 mg of fosmanogepix dose QD.
- Secondary endpoint: global response at EOST by participant who switch to 400 mg BID fosmanogepix dose vs. maintained with 800 mg of fosmanogepix dose QD.

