# 4.4.2 Patient Discontinuation Rules

Study treatment for an individual patient may be discontinued for lack of clinical and/or microbiological response, any adverse event, SAE, laboratory abnormality, or intercurrent illness which, in the opinion of the Investigator, indicates that continued dosing in the study is not in the best interest of the patient. Whenever feasible, the Investigator should discuss the patient situation with the Medical Monitor prior to discontinuation of the patient.

A patient who has discontinued study drug administration will still be encouraged to continue visits and assessments necessary for appropriate safety follow-up, and to complete the full panel of assessments scheduled for the E/T Visit. The reason for patient withdrawal must be documented in the eCRF.

In the case of patients lost to follow-up, attempts to contact the patient must be made and documented in the patient's medical records.

Withdrawn patients will not be replaced.

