# 5.5.3 Study Drug Administration

APX001 for IV administration will be delivered via central venous catheter (CVC) or peripheral IV line access according to SOC. APX001 for IV administration must not be infused into the same CVC or peripheral line access that is being used concurrently for the administration of other medications. Volumetric infusion pumps will be used during the administration of APX001 to ensure the prescribed volume is delivered to the patient. The infusion rate and total volume administered will be recorded on the patient's IV bag label and in their source documentation.

A loading dose of 1000 mg APX001 will be administered over 3 hours by IV infusion BID within the first 24 hours after initiation of the first infusion. On Days 2 and 3, 600 mg APX001 will be administered over 3 hours by IV infusion QD. From Day 4 through EOST, the IV dose remains 600 mg APX001 administered over 3 hours by IV infusion QD, or patients may be switched to PO administration of 800 mg APX001 QD.

Patients who have completed a minimum of 3 days of IV APX001 may be switched from IV to PO APX001 if they are able to ingest medication PO and the Investigator deems it is in the patient's best interest to do so. The switch to PO can be done on any day from Day 4 onwards. Patients will remain hospitalized for at least 2 days following the initial switch from IV to PO so that their tolerance to the oral medication may be evaluated and treated as necessary. Oral APX001 may be given with food, and prophylactic antiemetics may be administered. Patients may be switched between IV and PO as needed. Oral APX001 may be given as an outpatient.

Study drug will not be administered for longer than 6 weeks (inclusive of the loading dose [Day 1]). If an Investigator documents an improvement or resolution in clinical signs and symptoms prior to 6 weeks, eg, if follow-up imaging (as applicable) shows improvement; or a mycological response (if amenable to repeat sampling) is observed, the Investigator may choose to discontinue dosing. Patients will be requested to return for an EOST and Follow-Up Visit and to agree to a Follow-Up Phone Call. Patients who still require treatment after EOST should continue on OLAT.

Tablets are to be administered at the same time each day, whole, and taken by mouth with water. No splitting or crushing of tablets is allowed.

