3.2. Secondary Efficacy Endpoint(s) Assessed by DRC

The secondary efficacy parameter for this study is Global Response at EOST/ET. Global response will be classified as follows according to prespecified criteria, as determined by the DRC (Guidelines for the DRC are described in the DRC Charter):

- Complete Response: Survival within the prespecified period of observation, resolution of all attributable symptoms and signs of disease and radiological abnormalities, and mycological evidence of eradication of disease).
- Partial Response: Survival within the prespecified period of observation, improvement in attributable symptoms and signs of disease and radiological abnormalities, and evidence of clearance of cultures or reduction of fungal burden, as assessed by a quantitative and validated laboratory marker categorized as treatment success.
- Stable Response: Survival within the prespecified period of observation and minor or no improvement in fungal disease, but no evidence of progression, as determined based on a composite of clinical, radiological, and mycological criteria, progression of disease, or death (categorized as treatment failure).
- Progression of fungal disease: Evidence of progressive fungal disease based on a composite of clinical, radiological, and mycological criteria.

• Death: Death during the prespecified period of evaluation, regardless of attribution. If any patient has missing global response at EOST, it will be presented as 'Indeterminate' in the summary.

Treatment outcomes for Global Response based on DRC assessment at EOST are defined as follows:

- Treatment success: Complete response or partial response.
- Treatment failure: Stable response, progression of fungal disease and death.

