5.3.5. Analyses for Binary Endpoints

For all binary endpoints, proportion of participants and 95% CI will be presented.

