6.2. Main Analysis

All-cause mortality through Day 42 is calculated as the percentage of patients who die after the first dose of study drug through Day 42 from any cause using the mITT population.

For Cohort A only, the 1-sided exact binomial test at the alpha = 0.1 level of significance will be used to test the hypothesis as below:

H0: π ≥45%

Ha: $\pi < 45\%$

where π is the all-cause mortality through Day 42. 1-sided 90% confidence interval (CI) or two-sided 80% CIs will be provided. It can be concluded that the all-cause mortality at Day 42 is less than 45% (based on historical control data) if the upper limit of the CI is lower than 45%.

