6.8.5. Study Drug Exposure and Compliance

Study drug includes both intravenous and oral fosmanogepix. Days of exposure to study drug will be calculated as follows:

- Days of exposure Overall (IV + oral dose) as the last dose date of study drug first dose date of study drug +1.
- Days of exposure IV dose only (as the last dose date of IV the first dose date of IV) number of days that participant was switched to oral dose.
- Day of exposure oral dose only (as the last date of oral dose first date of oral dose) number of days that the participant was in IV dose.

Descriptive statistics with count and percentage of participants with overall (oral + iv dose), oral dose and iv dose, for cohort a based on the ITT/safety population and mITT population will be provided with exposure in the following categories:

- ≤14 days.
- >14 to ≤ 28 days.
- >28 to ≤ 42 days.
- >42 days.

For patients who switch from intravenous to oral dose, the compliance rate for oral dose will be calculated as the total amount of doses received divided by the total amount of doses expected then multiplied by 100. The total amount of expected doses is the number of medication days multiplied by the expected doses per day. Number of medication days is the total number of days from the date of the first oral dose of study drug to the date of the last oral dose of study drug. In addition for oral dose, for participant who switch from 800 mg/day QD to 400 mg BID, number and presence of participant will be provided.

For patients who did not switch from intravenous (IV) to oral dose, the compliance rate for IV dose will be calculated as the total amount of doses received divided by the total amount of doses expected then multiplied by 100. The total amount of expected doses is the number of medication days multiplied by the expected doses per day. Number of medication days is

the total number of days from the date of the first IV dose of study drug to the date of the last IV dose of study drug.

The overall study drug compliance will be the oral dose compliance plus the IV dose compliance.

Percent compliance with study drug will be calculated using the following formula:

%"compliance"= ("total amount of doses received * " 100)/"expected doses per day * the total number of medication days"

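### SAP 6.7 groups Day 42 mortality and EOST response by an on-treatment switch to 400 mg BID; if switching is unrelated to prognosis and has no effect, expected mortality is still lower in switchers

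*SAP*

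**What the plan says.** SAP 6.7 plans six subset analyses of the primary and key secondary endpoints. Four use the baseline pathogen or the limited-treatment-option criterion. The other two use the oral schedule: "Primary endpoint: Day 42 mortality by participant who switch to 400 mg BID fosmanogepix dose vs. maintained with 800 mg of fosmanogepix dose QD", and the same split for global response at EOST.

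SAP 6.8.5 shows that the switch is made during oral treatment: "for participant who switch from 800 mg/day QD to 400 mg BID, number and presence of participant will be provided". Protocol 5.5.3 sets the earliest oral dosing: "The switch to PO can be done on any day from Day 4 onwards". The protocol text describes only 800 mg QD by mouth. It gives no 400 mg BID regimen and no criteria for moving to one.

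Mortality under SAP 6.2 is "the percentage of patients who die after the first dose of study drug through Day 42 from any cause using the mITT population". Neither document defines the maintained group, sets a landmark day, or says where patients who never took oral drug belong. SAP Appendix 1 says only that all observed data are used. SAP 5.3.5 adds: "For all binary endpoints, proportion of participants and 95% CI will be presented".

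**The concern.** Group membership is settled after the mortality clock has started. To be a switcher, a patient must start oral drug and then live until the schedule changes. A patient who dies on 800 mg QD before that has no natural place except the maintained group. The switchers' death-free waiting time counts in their favour, which is immortal-time bias.

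At stake is how one table is read. Two mortality rates side by side, labelled by oral schedule, look like a comparison of BID with QD. With no effect of switching, and switching unrelated to prognosis, the expected difference is still not zero. A confidence interval around each rate covers sampling error and not the way the groups were formed. SAP 6.7 lists these splits with the four others and attaches no caveat.

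**Working it through.** **The plan's own figures.** With 24 mITT patients, the exact test at one-sided 0.1 rejects 45% at 7 or fewer deaths. P(X ≤ 7 | 0.45) = 0.0863 and P(X ≤ 7 | 0.20) = 0.9108, which agrees with the stated power above 90%; 24/0.60 = 40 dosed. The switch grouping does not enter this test.

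**Inputs.** From the documents: 20% mortality by Day 42, 24 mITT patients, oral dosing from Day 4. Assumed, because the documents give no share, timing or reason: constant hazard; oral start on Day 4 or uniform over Days 4–14; switch 1–3, 1–7, 1–21 or 7–21 days after oral start; 25% or 50% of patients destined to switch; switching unrelated to prognosis and without effect; IV-only patients left out. Day number is taken as elapsed time.

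**Formulas.** Survival to day t is 0.8^(t/42). For oral start s, delay d and destined share q:
- Switchers: 1 − 0.8^((42−s−d)/42).
- Destined to stay on QD: A = 1 − 0.8^((42−s)/42).
- Destined switchers who die before switching: B = 1 − 0.8^(d/42). All of them count as maintained deaths.
- Maintained: [(1−q)A + qB] / [(1−q) + qB].

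**One case by hand** (s = 4, d = 7, q = 0.5). Switchers: 1 − 0.8^(31/42) = 15.2%. A = 1 − 0.8^(38/42) = 18.3%. B = 1 − 0.8^(7/42) = 3.65%. Maintained: (0.0914 + 0.0183)/(0.5 + 0.0183) = 21.2%. The gap is 6.0 points. With d = 0 both groups are at 18.3% and the gap is zero.

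**Range**, averaging over the assumed timings:

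| Oral start | Delay (days) | Destined share | Switchers | Maintained | Gap (points) |
|---|---|---|---|---|---|
| Day 4 | 1–3 | 25% | 17.4% | 18.6% | 1.2 |
| Days 4–14 | 1–7 | 50% | 14.3% | 17.8% | 3.5 |
| Days 4–14 | 1–21 | 50% | 11.1% | 20.6% | 9.5 |
| Days 4–14 | 7–21 | 50% | 9.6% | 21.7% | 12.1 |

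The first and last rows are the extremes of the 16 scenarios.

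**Sensitivity.**
- If the hazard halves after oral start, the gap is 0.6 to 6.7 points.
- If 40% of lower-risk improvers stop within 21 days of oral start (start on Days 4–14), it is 0.9 to 9.4 points.
- With a fixed 7-day delay, Day 4 start and 50% destined, a falling hazard (Weibull shape 0.7) gives 12.8% against 19.9%, and a rising one (shape 1.5) gives 17.5% against 21.4%.

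**Noise.** With about 11 patients per group and 18% mortality, the SD of the difference is about √(2 × 0.18 × 0.82/11) = 0.16. Simulated trials of 24 gave 15 to 19 points. The share of such trials with the lower rate in switchers was 0.556 in the mildest case, against 0.528 with random labels of the same group sizes. In the strongest case it was 0.767 against 0.483.

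**Prognosis.** With Day 4 start, a 7-day delay and 30% destined to switch, a hazard ratio of 1.5 in destined switchers reverses the gap: 19.2% in switchers, 17.8% in maintained. For delays of 1–3 or 1–7 days, a hazard ratio of about 1.1 to 1.3 cancels it. The latest timings with a 50% share need about 4.

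**EOST response.** Deaths before a switch are failures in the maintained group ("Treatment failure: Stable response, progression of fungal disease and death"). Early stopping also leaves patients there. On improvement, "the Investigator may choose to discontinue dosing" (Protocol 5.5.3), which puts successes in it. Protocol 4.4.2 puts failures in it: "Study treatment for an individual patient may be discontinued for lack of clinical and/or microbiological response". With 20% mortality, 40% or 60% response, 50% destined to switch and delays of 1–7, 1–21 or 7–21 days, success in switchers minus maintained is:
- deaths only: +1.4 to +7.4 points;
- 40% of responders stopping early: −2.1 to −8.7;
- 40% of non-responders stopping early: +4.4 to +17.7.

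**Landmark check.** Grouping by schedule at Day 14 among those alive, and counting only later deaths, gives 1 − 0.8^(28/42) = 13.8% in both groups, so the artefact disappears.

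**The case against.** The strongest reply is that the display is descriptive. No hypothesis, test or decision rule attaches to it, and noise of 15 to 19 points exceeds the tilt in every scenario. The larger gaps need switching one to three weeks after oral start, which no document supports; short delays give 1.2 to 3.5 points. A schedule change made during treatment is also unlikely to be random, and a modest excess risk in switchers would cancel a small tilt. A caveat and a definition of the maintained group might then be enough.

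Most of this stands, and it is why the point is minor. It does not make the grouping sound. If prognosis drives switching, the table mixes two distortions of unknown net sign and is harder to read. Noise can hide the tilt in one trial but does not remove it.

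A reader might infer that the table will show switchers doing better. The documents do not support that, because they give neither the reason for switching nor its timing. Counting pre-switch deaths as maintained is itself the natural reading and not a stated rule.

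**Conclusion.** The concern holds, as a minor one. Followed as written, SAP 6.7 forms groups on a post-baseline event and counts deaths from first dose. If switching is unrelated to prognosis and has no effect, expected mortality is about 1 to 12 points lower in switchers at 20% overall mortality. Only the 20%, the 24 patients and the Day 4 limit come from the documents; the delays, shares and hazard shape are assumptions. If switching depends on prognosis, the net sign is unknown.

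Two stronger readings should be resisted. The EOST split is also post-baseline, but it does not share a known direction of bias: the results run from −8.7 to +17.7 points according to who stops early. Nor is the primary conclusion compromised, since the test against 45% uses all mITT patients whatever their oral schedule.

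**What to change.** In SAP 6.7, replace the two switch-versus-maintained rate displays with a listing of switchers: switch date, reason where recorded, Day 42 status and EOST response. State that the grouping is post-baseline and is not a comparison of schedules.

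If a grouped table is kept:
- define the maintained group;
- limit the table to oral-treated patients and show IV-only patients separately;
- fix the landmark day in the SAP before database lock, without reference to outcomes;
- count only deaths after the landmark;
- carry the same caveat.

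The cost is SAP wording and the loss of a side-by-side summary. The landmark table would be thin. With oral start on Days 4–14 and 20% mortality, a Day 14 landmark leaves about 1.1 to 2.3 switchers of 24 for delays of 1–21 days, and 0.2 to 0.4 for 7–21 days. A Day 28 landmark leaves about 4 to 10. At the upper end that is 24 × 0.5 × 0.8^(28/42) = 10.3 switchers, with 10.3 × (1 − 0.8^(14/42)) = 0.7 later deaths expected. The listing is therefore the better choice.

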6.8. Baseline and Other Summaries and Analyses

For continuous baseline variables, the number of observations (n), mean, standard deviation, median, minimum, and maximum will be provided. For baseline categorical variables, the frequency and percentage in each category will be displayed. Baseline Summaries.

The following demographic and baseline characteristics will be summarized:

- Age (years) and age categories (<65 years vs. ≥65 years).
- Sex.
- Race.
- Ethnicity.
- Height (cm).
- Weight (kg).
- Body mass index (BMI) (kg/m²).
- eGFR (ml/min /1.73 m²) calculated by CKD-EPI equation and categories (<30, 30-<60, 60-<90 and ≥90).

- Eastern cooperative oncology group (ECOG) status (0, 1, 2, 3, 4, and 5).
- Severity of disease assessed by Karnofsky performance status and categories (≤30 vs. >30).
- Hospitalization status (ICU, non-ICU, emergency room, or other).
- Diagnosis of IMI per DRC (possible IMI, probable IMI, proven IMI, and not categorized).
- Site of IMI as below:
 - Cerebral.
 - Cutaneous abscess.
 - Eye.
 - Intraabdominal.
 - Pulmonary.
 - Renal.
 - Sinuses.
 - Thrombus.
 - Urogenital.
 - Other.
- Limited Treatment Options Criteria:
 - Documented or anticipated resistance.
 - Contraindication to soc.
 - Intolerance to soc.
 - Lack of clinical response to soc.
 - No treatment options.

Demographic and baseline characteristics will be summarized with descriptive statistics or counts and percentages of patients as appropriate by Cohort A for the ITT/Safety Population, mITT, Populations.

6.8.1. Baseline Infection Characteristics

All baseline pathogens will be summarized with counts and percentages of patients in total for the mITT Populations.

Details of organism identification and antifungal susceptibility results including MICs of all antimicrobials tested will be listed by patient. Data from both local and central microbiological laboratories will be listed.

6.8.2. Medical History

Medical history will be coded to SOC and PT using the Medical Dictionary for Regulatory Activities (MedDRA, Version 25.0). Counts and percentages of patients with medical history by SOC and PT will be summarized for Cohort A based on the ITT/Safety Population and mITT Population. Medical history will be listed by patient.

6.8.3. Study Conduct and Participant Disposition

Patient disposition will be summarized for the ITT/Safety Population and mITT Population by Cohort A. The following patient disposition categories will be included in the summary:

- Patients who received study drug.
- Patients who completed the study drug.
- Patients who did not complete the study drug (and reason).
- Patients who did not complete the study drug due to the impacts of the covid-19 pandemic.
- Patients who completed the study through Day 42.
- Patients who did not complete the study through Day 42.
- Patients who completed the study through the follow-up visit (4 weeks after EOST).
- patients who did not complete the study (and reason).

For patients who did not complete study drug and patients who did not complete the study, a summary of reasons for discontinuation will be provided. In addition, the total number of patients for each defined population will be tabulated.

6.8.4. Protocol Deviations

The number of patients with at least one protocol deviation, and the number of patients with at least one deviation in each category defined in the study protocol deviation plan. Deviations will be presented for Cohort A by category for important protocol deviations based on the ITT/Safety Population and mITT Population. In addition, the protocol deviations related to COVID-19 pandemic will be categorized and summarized separately. Protocol deviations will also be listed by patient.

6.8.5. Study Drug Exposure and Compliance

Study drug includes both intravenous and oral fosmanogepix. Days of exposure to study drug will be calculated as follows:

- Days of exposure Overall (IV + oral dose) as the last dose date of study drug first dose date of study drug +1.
- Days of exposure IV dose only (as the last dose date of IV the first dose date of IV) number of days that participant was switched to oral dose.
- Day of exposure oral dose only (as the last date of oral dose first date of oral dose) number of days that the participant was in IV dose.

Descriptive statistics with count and percentage of participants with overall (oral + iv dose), oral dose and iv dose, for cohort a based on the ITT/safety population and mITT population will be provided with exposure in the following categories:

- ≤14 days.
- >14 to ≤ 28 days.
- >28 to ≤ 42 days.
- >42 days.

For patients who switch from intravenous to oral dose, the compliance rate for oral dose will be calculated as the total amount of doses received divided by the total amount of doses expected then multiplied by 100. The total amount of expected doses is the number of medication days multiplied by the expected doses per day. Number of medication days is the total number of days from the date of the first oral dose of study drug to the date of the last oral dose of study drug. In addition for oral dose, for participant who switch from 800 mg/day QD to 400 mg BID, number and presence of participant will be provided.

For patients who did not switch from intravenous (IV) to oral dose, the compliance rate for IV dose will be calculated as the total amount of doses received divided by the total amount of doses expected then multiplied by 100. The total amount of expected doses is the number of medication days multiplied by the expected doses per day. Number of medication days is

the total number of days from the date of the first IV dose of study drug to the date of the last IV dose of study drug.

The overall study drug compliance will be the oral dose compliance plus the IV dose compliance.

Percent compliance with study drug will be calculated using the following formula:

%"compliance"= ("total amount of doses received * " 100)/"expected doses per day * the total number of medication days"

The compliance rate will be summarized with descriptive statistics overall (Oral + IV) dose, oral dose, and IV dose for Cohort A for the ITT/Safety Population and mITT Population. In addition, contingency tables will be provided to show the number and percentage of patients with compliance in the following categories: <80% and $\ge80\%$.

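### SAP 6.8.5 can misstate exposure and compliance in the descriptive tables: route exposure lacks the +1, switchers have no IV rate, overall compliance is worded as a sum, and IV days can count as missed oral doses

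*SAP*

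**What the plan says.** All the rules are in SAP 6.8.5, Study Drug Exposure and Compliance.

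- **Exposure.** Overall days are the last dose date minus the first dose date, plus 1. The IV-only line reads "as the last dose date of IV the first dose date of IV) number of days that participant was switched to oral dose", with no +1. The oral-only line has the same form. The bands are up to 14, over 14 to 28, over 28 to 42, and over 42 days, tabulated overall and by route.
- **Route compliance.** "For patients who switch from intravenous to oral dose, the compliance rate for oral dose will be calculated" as doses received over doses expected, times 100. "For patients who did not switch from intravenous (IV) to oral dose, the compliance rate for IV dose will be calculated" in the same way. No IV rate is given for patients who switch.
- **Denominator.** "The total amount of expected doses is the number of medication days multiplied by the expected doses per day". For the oral rate, "Number of medication days is the total number of days from the date of the first oral dose of study drug"; the final oral dose closes this span.
- **Overall compliance.** "The overall study drug compliance will be the oral dose compliance plus the IV dose compliance". Next comes "Percent compliance with study drug will be calculated using the following formula": doses received times 100, over expected doses per day times medication days.
- **Output.** Overall, oral and IV rates are all to be summarised, with a table split at 80%.

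Protocol 5.5.3 gives two 1000 mg infusions in the first 24 hours, then once-daily IV dosing, with oral dosing possible from Day 4. Protocol 3.1, Table 1 and 5.5.3 allow switching between routes as needed.

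**The concern.** A programmer who follows these sentences as written gets results that are wrong or undefined for some ordinary treatment courses. One patient can appear in two exposure bands for the same days. A switcher has no IV rate, so the overall rate has no stated IV component. A patient who missed nothing can fall below the 80% line, and one who missed many doses can appear above it.

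These tables are specified for both the ITT/Safety and mITT populations, and the numbers are small. With about 40 dosed patients in Cohort A, one misplaced patient moves a cell by 1/40 = 2.5 percentage points. With the planned 24 in the mITT population, it moves by 1/24 = 4.2 points. The compliance table is where a reader looks to judge whether the regimen was actually taken.

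**Working it through.** The documents state no compliance or exposure result, so there is no figure to reproduce. I applied the SAP 6.8.5 rules to assumed dosing histories within the 42-day maximum and compared them with a direct count. The minus signs are missing from the exposure lines as extracted; I read them in and do not count their absence as an error. The +1 survives in the overall line and is absent from both route lines.

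**1. Exposure.** Overall = last − first + 1. Route = (last − first) − other-route days.

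- IV only, Days 1–15: overall 15 − 1 + 1 = 15 (over 14 to 28); IV 15 − 1 − 0 = 14 (up to 14).
- IV only, Days 1–29: overall 29 (over 28 to 42); IV 28 (over 14 to 28).
- For patients who never switch, these are the only two durations up to 42 days at which the band changes. At 43 days it would change again, but that is past the treatment maximum.
- IV Days 1–7, then oral Days 8–42, subtracting only other-route days inside each route's span: IV 7 − 1 − 0 = 6 and oral 42 − 8 − 0 = 34. The true values are 7 and 35, and the total is 40 instead of 42.
- On the same in-span reading, IV Days 1–13 then oral Days 14–42 gives oral 42 − 14 = 28 against a true 29, which is again a band change.
- The text does not limit the subtraction to the route's own span. Subtracting all other-route days for IV 1–7, oral 8–42 would give IV 6 − 35 = −29 and oral 34 − 7 = 27.

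**2. Switchers' IV rate.** Every patient starts on IV, so every patient who takes oral drug is a switcher. A switcher has an oral rate only. If overall then falls back to that rate, IV 36/36 (Days 1–35) and oral 5/7 (Days 36–42) gives 71.4%. Pooled, it is (36 + 5)/(36 + 7) = 41/43 = 95.3%.

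**3. The sum.** This step assumes that an IV rate is also computed for switchers.

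| IV | Oral | Percentages added | Doses pooled |
|---|---|---|---|
| 8/8 | 35/35 | 200% | 43/43 = 100% |
| 6/8 | 24/35 | 75.0 + 68.6 = 143.6% | 30/43 = 69.8% |
| 8/8 | 21/35 | 100 + 60 = 160% | 29/43 = 67.4% |

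The last two rows cross the 80% line. For a patient on one route only, the two readings agree.

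**4. IV days inside the oral span.** Let S be the days from first to last oral dose and k the IV days between them. With nothing missed and only oral doses counted as received, the oral rate is (S − k)/S. It falls below 80% when k > 0.2 × S. For S = 35, k = 7 gives 28/35 = 80.0% and k = 8 gives 27/35 = 77.1%. On the days actually assigned to oral, the second patient has 27/27 = 100%.

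**5. Expected doses per day (conditional).** If one constant is used and doses are counted by number, IV-only dosing for 42 days with nothing missed gives 43/42 = 102.4% at one per day, because of the second loading infusion. The SAP also tabulates oral regimen changes, "for participant who switch from 800 mg/day QD to 400 mg BID". With 14 days of each and nothing missed, 14 + 28 = 42 doses. That is 42/28 = 150% at one per day, or 42/56 = 75% at two.

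**The case against.** The strongest reply is that much of this depends on an unhelpful reading. SAP 6.8.5 defines study drug as both routes together, so the closing percent-compliance formula can be taken as pooled. The plus sign in the labels for the overall columns also plainly means the two routes combined. That has force. A reader might infer that the SAP definitely adds two percentages and will report 160% or 200%; the documents do not settle that. What stands is that the sentence defining overall compliance joins two quantities already defined as percentages, and never says that doses are pooled.

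Three other narrowings are fair.

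- A reader might infer that any return to IV counts against the patient. It does not. IV days enter the oral denominator only if the patient later resumes oral, and they lower the rate only if oral doses alone count as received.
- The −29 figure follows from a subtraction no programmer would accept. It shows that the span is unstated, not what the SAP intends.
- The SAP never says that expected doses per day is a constant. If amounts are counted in milligrams, the change from 800 mg once daily to 400 mg twice daily leaves the daily total unchanged, and the 150% and 75% figures disappear.

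It could also be said that the +1 was lost in text extraction with the minus signs. Its survival in the overall line makes this unlikely, though the published file should be checked.

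None of this supplies an IV rate for switchers or explains the missing +1.

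**Conclusion.** The point holds as a minor error of specification, confined to descriptive tables. Three parts rest on the wording itself: the route exposure formulas are one day short for patients who never switch; switchers have no defined IV compliance rate although IV and overall summaries are required; and the overall sentence is wrong if taken literally. The oral-span problem is real under the two conditions given above. The expected-dose problem is conditional on a single constant and on counting doses by number.

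The sizes come from assumed dosing histories. How many patients would change category cannot be known from the documents.

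A reader might infer that efficacy conclusions are at risk, because the Per-Protocol definition in SAP section 4 requires at least 80% of intended doses. The documents do not support that. The same table says that Per-Protocol analyses will not be performed, and the Day 42 mortality test is run on the mITT population, whose definition does not involve compliance.

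**What to change.** Amend SAP 6.8.5 as follows.

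- **Overall compliance:** replace the sum with 100 × (IV + oral doses received) / (IV + oral doses expected).
- **Route rates:** define IV and oral compliance for every patient who used that route, switchers included, on days assigned to that route only. Let expected doses follow the regimen in use on each day, including both loading infusions. State how a switch day, and a wholly missed day at a switch, is assigned.
- **Route exposure:** use last − first + 1, minus only the other-route days inside that route's own span.

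Check of the exposure rule: IV Days 1–7, oral Days 8–42 gives 7 − 1 + 1 = 7 and 42 − 8 + 1 = 35, total 42. With IV Days 1–7 and 15–22, and oral Days 8–14 and 23–42, it gives IV 22 − 1 + 1 − 7 = 15 and oral 42 − 8 + 1 − 8 = 27, total 42.

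The 400 mg twice-daily oral dosing in SAP 6.7 and 6.8.5 and the 800 mg once-daily oral dosing in the protocol must be reconciled so that expected doses are defined. This point takes no position on which applies.

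The cost is a few sentences and a little programming. Route and regimen are needed for each dosing day; for outpatients these come from the dosing diary in Protocol 5.5.4. The design, the primary analysis and the adverse event tables are unchanged.
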